7.4 Storage

All study drugs should be kept in a secure place under appropriate storage conditions (at room temperature). The IP label on the bottle specifies the appropriate storage.

7.5 Compliance

The administration of all study drugs (including IPs) should be recorded in the appropriate sections of the eCRF.

Patients should be given clear instructions on how and when to take their study treatment. Patients will self-administer study treatment. Study site staff will make tablet counts at regular intervals during treatment. Compliance will be assessed by the tablet count and the information will be recorded in the appropriate section of the eCRF. After the tablet count has been performed, the remaining tablets will not be returned to the patient but will be retained by the investigative site until reconciliation is completed by the study monitor. All patients must return their bottle(s) of study treatment at the appropriate scheduled visit, when a new bottle will be dispensed. Patients will be instructed to notify study site personnel of missed doses. Dates of missed or held doses will be recorded by the site staff on the eCRF.

Patients must return all containers and any remaining tablets at the end of the study.

7.6 Accountability

The study drug provided for this study will be used only as directed in the Clinical Study Protocol.

The study site staff will account for all study drugs dispensed to and returned from the patient.

At the end of the study, it must be possible to reconcile delivery records with records of usage and destroyed/returned stock. Records of usage should include the ID of the person to whom the study treatment was dispensed, the quantity and date of dispensing and unused study treatment returned to the Investigator. This record is in addition to any drug accountability information recorded on the eCRF. Any discrepancies must be accounted for on the appropriate forms. Certificates of delivery and return must be signed, preferably by the Investigator or a pharmacist, and copies retained in the Investigator site file. Dispensing and accountability records will continue to be collected for as long as patients continue to receive study treatment, although they will not be entered on the database after the database has closed. Study site personnel, if applicable, or the AstraZeneca monitor will account for all study drugs received at the site, unused study drugs and for appropriate destruction. Certificates of delivery, and destruction should be signed.

7.7 Concomitant and other treatments

The use of any natural/herbal products or other traditional remedies should be discouraged, but use of these products, as well as use of all vitamins, nutritional supplements, and all other concomitant medications must be recorded in the eCRF.

Medications that may NOT be administered (All Treatment Arms)

No other anti-cancer therapy (chemotherapy, immunotherapy, hormonal therapy (hormone replacement therapy is acceptable), radiotherapy, biological therapy or other novel agent) is to be permitted while the patient is receiving study medication.

Live virus and live bacterial vaccines should not be administered whilst the patient is receiving study medication and during the 30-day follow up period. An increased risk of infection by the administration of live virus and bacterial vaccines has been observed with conventional chemotherapy drugs and the effects with olaparib are unknown.

Restricted concomitant medications

Olaparib:

Strong or Moderate CYP3A inhibitors

Known strong CYP3A inhibitors (eg, itraconazole, telithromycin, clarithromycin, boosted protease inhibitors, indinavir, saquinavir, nelfinavir, boceprevir, telaprevir) or moderate CYP3A inhibitors (ciprofloxacin, erythromycin, diltiazem, fluconazole, verapamil) should not be taken with study treatment.

If there is no suitable alternative concomitant medication then the dose of study treatment should be reduced for the period of concomitant administration. The dose reduction of study treatment should be recorded in the eCRF with the reason documented as concomitant CYP3A inhibitor use.

- Strong CYP3A inhibitors – reduce the dose of olaparib to 100 mg bd for the duration of concomitant therapy with the strong inhibitor and for 5 half-lives afterwards.

- Moderate CYP3A inhibitors - reduce the dose of olaparib to 150 mg bd for the duration of concomitant therapy with the moderate inhibitor and for 3 half-lives afterwards.
- After the washout of the inhibitor is complete, the study treatment dose can be re-escalated.

Strong or moderate CYP3A inducers

Strong (eg, phenobarbital, phenytoin, rifampicin, rifabutin, rifapentine, carbamazepine, nevirapine, enzalutamide and St John's Wort) and moderate CYP3A inducers (eg. bosentan, efavirenz, modafinil) of CYP3A should not be taken with study treatment.

If the use of any strong or moderate CYP3A inducers are considered necessary for the patient's safety and welfare this could diminish the clinical efficacy of olaparib.

If a patient requires use of a strong or moderate CYP3A inducer then they must be monitored carefully for any change in efficacy of study treatment.

Permeability glycoprotein (P-gp) inhibitors

It is possible that co-administration of P-gp inhibitors (eg amiodarone, azithromycin) may increase exposure to olaparib. Caution should therefore be observed.

Effect of olaparib on other drugs

Based on limited *in vitro* data, olaparib may increase the exposure to substrates of CYP3A4, P-gp, OATP1B1, OCT1, OCT2, OAT3, MATE1 and MATE2K.

Based on limited *in vitro* data, olaparib may reduce the exposure to substrates of CYP3A4, 2B6, 2C9, 2C19 and P-gp.

The efficacy of hormonal contraceptives may be reduced if co administered with olaparib.

Caution should therefore be observed if substrates of these isoenzymes or transporter proteins are co-administered.

Examples of substrates include:

- CYP3A4 – hormonal contraceptive, simvastatin, cisapride, cyclosporine, ergot alkaloids, fentanyl, pimozide, sirolimus, tacrolimus and quetiapine.
- CYP2B6 – bupropion, efavirenz.
- CYP2C9 – warfarin.
- CYP2C19 - lansoprazole, omeprazole, S-mephenytoin.

- P-gp - simvastatin, pravastatin, digoxin, dabigatran, colchicine.
- OATP1B1 - bosentan, glibenclamide, repaglinide, statins and valsartan.
- OCT2 - serum creatinine.

Ceralasertib

Ceralasertib is an investigational drug for which potential interaction is considered on the basis of preclinical *in vitro* data only. As ceralasertib is being administered in combination with Olaparib, potential interactions of the Olaparib should also be considered.

The principal enzyme for metabolising ceralasertib is CYP3A, with some contribution by CYP2C8.

- If the use of any strong inhibitors of CYP3A and/or CYP2C8 is considered necessary for the patient's safety and welfare, the investigator must interrupt ceralasertib for the duration of concomitant therapy with the CYP3A and/or CYP2C8 inhibitor and required washout period (5 half-lives for strong and moderate CYP3A inhibitors). If the use of any strong inducers of CYP3A and/or CYP2C8 is considered necessary for the patient's safety and welfare, this may diminish the clinical efficacy of ceralasertib and the patient should be monitored for any change in the efficacy of study treatment.
- Ceralasertib is a Pgp substrate. Co-administration of Pgp inhibitors or inducers may affect exposure to ceralasertib and, therefore, should not be coadministered with ceralasertib. If the use of any inhibitors or inducers of Pgp are considered necessary for the subject's safety and welfare, the investigator must interrupt ceralasertib for the duration of the Pgp inhibitor or inducer and wait for the required wash-out period of the Pgp modulator (five half-lives) before dosing ceralasertib again.
- Ceralasertib is also a substrate of BCRP. Co-administration of BCRP inhibitors or inducers may affect exposure to ceralasertib; therefore, it is recommended that the investigators must interrupt ceralasertib for the duration of the BCRP inhibitor or inducer and wait for the required wash-out period of the BCRP modulator (five half-lives) before dosing ceralasertib again.
- Ceralasertib is a potential inducer of CYP3A4 and CYP2B6. Caution should be applied with coadministration of drugs that are either completely metabolized by CYP3A4 and/or CYP2B6, or that are substrates of CYP3A4 and/or CYP2B6 and also have a narrow therapeutic index. Investigators should be aware that the exposure of other drugs metabolised by CYP3A4 and/or CYP2B6 may be reduced.
- Ceralasertib is an inhibitor of OATP1B1 and BCRP. Caution should be applied with coadministration of substrates of OATP1B1 and/or BCRP as ceralasertib may increase their exposure.

If the use of any strong inducers or inhibitors of CYP3A4 and/or CYP2C8 is considered necessary for the patient's safety and welfare, the Investigator must contact the trials office and a decision to allow the patient to continue in the study will be made on a case-by-case basis.

A non-exhaustive list of restrictive and/or prohibited drugs is provided in [Appendix I](#)

AZD1775 - Not applicable following CSPv6.0

For concomitant and other treatments in combination with AZD1775 see [Appendix H](#).

All Treatment Arms:

Anticoagulant therapy

Patients who are taking warfarin may participate in this study; however, it is recommended that INR be monitored carefully at least once per week for the first month, then monthly if the INR is stable. Subcutaneous heparin, low molecular weight heparin and non-vitamin K antagonist oral coagulants (NOACs) are permitted.

Haematological support

Haematological toxicity should be appropriately managed as outlined in section 6.8.1. Blood / platelet transfusions may be given at the discretion of the Investigator according to local hospital guidelines, and recorded in the eCRF. The use of erythropoietin is not permitted. Intravenous iron is permitted if required by a patient on study, but not prior to dosing.

Primary prophylaxis with G-CSF is not permitted. However, if a patient develops febrile neutropenia, study treatments should be stopped and appropriate management including G-CSF should be given according to local hospital guidelines (see Section [6.8.1.2](#)).

Anti-emetics/anti-diarrhoeals

From screening part 2 onwards, should a patient develop nausea, vomiting and / or diarrhoea, then these symptoms should be reported as AEs (see Section [6.3](#)) and appropriate treatment of the event given. Antiemetic prophylaxis as mandated by the protocol should be recorded as concomitant medication. Please note: aprepitant (Emend) and fosaprepitant are not permitted in the olaparib+AZD1775 treatment arm due to known DDIs - **No longer applicable following CSPV6.0, provided there has been a minimum washout period of 10 days since the final dose of AZD1775.**

Palliative radiotherapy

Palliative radiotherapy may be used for the treatment of pain at the site of bony metastases that were present at baseline, provided the Investigator does not feel that these are indicative of clinical disease progression during the study period. Study treatment should be discontinued for a minimum of 3 days before a patient undergoes therapeutic palliative

radiation treatment. Study treatment should be restarted within 4 weeks as long as any bone marrow toxicity has recovered.

Administration of other anti-cancer agents

Patients must not receive any other concurrent anti-cancer therapy, including investigational agents, while on study treatment. Patients may continue the use of bisphosphonates or denosumab for bone disease as long as these were started at least 5 days prior to study treatment. If on corticosteroids for the symptomatic control of brain metastases, the patient should be receiving a stable dose of corticosteroids started at least 4 weeks prior to treatment.

Subsequent therapies for cancer

Details of first and subsequent therapies for cancer and/or details of surgery for the treatment of the cancer, after discontinuation of treatment, will be collected. Reasons for starting subsequent anti-cancer therapies including access to other PARP inhibitors or investigational drugs will be collected and included in the assessments of OS.

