RIT=Ritonivir. Ritonavir has dual effects of simultaneous CYP3A inhibition and induction, and the net pharmacokinetic outcome during chronic ritonavir therapy is inhibition of CYP3A activity

[1] VIEKIRA PAK = 150/100 mg paritaprevir/ritonavir + 25 mg ombitasvir + 800 mg dasabuvir for 28 days. [2]. Double-strength grapefruit juice. Patients should abstain from eating large amounts of grapefruit and Seville oranges (and other products containing these fruits e.g., grapefruit juice or marmalade) during the study (e.g., no more than a small glass of grapefruit juice (120 mL) or half a grapefruit or 1-2 teaspoons (15 g) of Seville orange marmalade daily

App. Table 6: Drugs known to be inhibitors and inducers of CYP2C8

Potent CYP2C8 inhibitors	Potent CYP2C8 inducers
gemfibrozil clopidogrel	None identified

List created using the University of Washington Drug-Drug Interaction Database Jan 2020.

Drugs known to be inhibitors or inducers of Pgp and/or BCRP, undertake appropriate monitoring if coadministration is necessary

Ceralasertib is a substrate of Pgp and BCRP. Co-administration of Pgp inhibitors/inducers or BCRP inhibitors/inducers may affect exposure to ceralasertib therefore it is recommended that these are not co-administered with ceralasertib.

These lists are not intended to be exhaustive, and similar restrictions will apply to other agents that are known to modulate Pgp activity or BCRP activity. Please contact AstraZeneca with any queries you have on this issue. Please refer to full prescribing information for all drugs prior to co-administration with ceralasertib.

App. Table 7: Drugs known to be inhibitors or inducers of P-gp

Drugs Known to be Inhibitors of Pgp ^a	Drugs Known to be Inducers of Pgp ^b
Amiodarone azithromycin captopril carvedilol clarithromycin conivaptan cremophor curcumin diltiazem dronedarone elacridar erythromycin felodipine fluvoxamine ginkgo indinavir itraconazole ketoconazole lapatinib lopinavir and ritonavir mibefradil milk thistle mirabegron nelfinavir nifedipine nitrendipine paroxetine quercetin quinidine ranolazine rifampin ritonavir saquinavir/ritonavir schisandra chinensis extract St Johns Wort talinolol telaprevir telmisartan ticagrelor tipranavir/ritonavir tolvaptan valsopodar (PSC 833) verapamil	avasimibe carbamazepine efavirenz genistein phenytoin rifampin St Johns Wort

a. Inhibitors listed for P-gp are those that showed >25% increase in exposure to a P-gp substrate (e.g. digoxin).

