b. Inducers listed for P-gp are those that showed >20 % decrease in exposure to a P-gp substrate (e.g. digoxin)

App. Table 8: Drugs known to be inhibitors or inducers of BCRP

Drugs Known to be Inhibitors of BCRP	Drugs Known to be inducers of BCRP
Afatinib Aripiprazole Curcumin Cyclosporine Elacridar Erlotinib Fluvastatin Fumitremorgin Gefitinib Ivermectin Lapatinib Nilotinib Novobiocin Pantoprazole Pitavastatin Ponatinib Quercetin Quizartinib Rabeprazole Regorafenib Rilpivirine Sulfasalazine Sunitinib Tacrolimus Teriflunomide Trametinib Trifluoperazine Vismodegib eltrombopag Atazanavir Lopinavir Ritonavir Tipranavir Omeprazole Estrone 17b-estradiol Imatinib mesylate	Please check individual drugs on a case by case basis

List created using <http://dmd.aspetjournals.org/content/dmd/43/4/490.full.pdf>

Note: Although BCRP is involved in a number of clinically relevant DDIs, none of the cited inhibitors above is truly specific for this transporter

Drugs known to be substrates of CYP3A4 and/or CYP2B6, undertake appropriate monitoring if coadministration is necessary

Ceralasertib is a potential inducer of CYP3A4 and CYP2B6. Therefore caution should be applied with co administration of drugs that are either completely metabolised by CYP3A4 and/or CYP2B6, or that are substrates of CYP3A4 and/or CYP2B6 and also have a narrow therapeutic index. Investigators should be aware that the exposure of other drugs metabolised by CYP3A4 and/or CYP2B6 may be reduced.

App. Table 9: Drugs known to be metabolised by CYP3A4 and have a narrow therapeutic index

Alfentanil Cyclosporine Dihydroergotamine Ergotamine Fentanyl Pimozide Quinidine Sirolimus Tacrolimus Astemizole Cisapride Terfenadine

App. Table 10: Drugs known to be metabolised by CYP2B6 and have a narrow therapeutic index

Cyclophosphamide Ifosfamide Efavirenz Bupropion Propofol Thiotepa Sorafenib alfentanil ketamine methadone methoxetamine nevirapine propofol selegiline sertraline sorafenib tamoxifen valproic acid
--

From Flockhart DA (2007). "Drug Interactions: Cytochrome P450 Drug Interaction Table". Indiana University School of Medicine

Drugs known to be substrates of OATP1B1 and BCRP, undertake appropriate monitoring if coadministration is necessary

Ceralasertib is also an inhibitor of OATP1B1 and BCRP. Caution should be applied with coadministration of substrates of OATP1B1 and/or BCRP as ceralasertib may increase their exposure.

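### Appendix I conflicts with the main protocol on two instructions: giving ceralasertib with a necessary P-gp modulator, and allowing grapefruit juice and Seville orange marmalade

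*Protocol*

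**What the plan says.** **P-gp.** Section 7.7 (Ceralasertib) says P-gp inhibitors and inducers should be avoided. If one is needed, "the investigator must interrupt ceralasertib for the duration of the Pgp inhibitor or inducer and wait for the required wash-out period", given as five half-lives. Section 7.7 then refers to Appendix I for a non-exhaustive list of drugs. In Appendix I the list of P-gp and BCRP modulators is headed "Drugs known to be inhibitors or inducers of Pgp and/or BCRP, undertake appropriate monitoring if coadministration is necessary". The paragraph under that heading says these agents may alter ceralasertib exposure, "therefore it is recommended that these are not co-administered with ceralasertib".

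**BCRP.** Section 7.7 says "it is recommended that the investigators must interrupt ceralasertib for the duration of the BCRP inhibitor or inducer", again with five half-lives. The Appendix I heading just quoted covers BCRP too.

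**CYP2C8.** For a necessary strong inhibitor, Section 7.7 says "the investigator must interrupt ceralasertib for the duration of concomitant therapy with the CYP3A and/or CYP2C8 inhibitor and required washout period". It later adds that for strong CYP3A4 or CYP2C8 inhibitors or inducers "the Investigator must contact the trials office and a decision to allow the patient to continue in the study will be made" case by case. Appendix I asks only for caution with potent CYP2C8 inhibitors or inducers and invites queries to the sponsor.

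**Grapefruit and Seville orange.** Section 3.7.1 prohibits grapefruit juice and Seville oranges, including marmalade, for all patients while in the study. Footnote 2 to App. Table 5 asks patients to avoid large amounts and gives daily limits of 120 mL of grapefruit juice, half a grapefruit, or 15 g of Seville orange marmalade.

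**The concern.** These are dosing and dietary instructions for an investigational drug in the only combination arm still recruiting. Section 7.7 and Appendix I agree on the default for P-gp modulators, which is to avoid them. They part when the drug cannot be avoided, which is when a site needs an instruction. A site working from Section 7.7 stops ceralasertib. A site working from the Appendix I heading could continue it under monitoring. One patient loses doses; a similar patient elsewhere is exposed to an interaction that the main text treats as serious enough to require interruption.

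The situation is plausible. Exclusion criteria 11 and 12 deal with CYP3A inhibitors and inducers, not P-gp modulators as a class. App. Table 7 lists drugs those criteria do not name, such as carvedilol, captopril, telmisartan, nifedipine and amiodarone.

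The grapefruit footnote is simpler: a patient advised from it could take daily amounts of juice or marmalade that Section 3.7.1 forbids.

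**Working it through.** The plan states no figure to reproduce. The check sets the current texts side by side.

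| Item | Main protocol | Appendix I | Result |
|---|---|---|---|
| P-gp modulator, default | Avoid (7.7) | Recommended against (body text) | Agree |
| P-gp modulator, necessary | Must interrupt, plus five half-lives (7.7) | Monitor (heading); no interruption or wash-out in the text available | Conflict |
| BCRP modulator, necessary | Recommended and must in the same clause (7.7) | Monitor (same heading) | Strength of 7.7 unclear; differs from the heading |
| Strong CYP2C8 inhibitor, necessary | Must interrupt; contact trials office (7.7) | Caution; queries to sponsor | Mismatch, contained |
| Grapefruit juice | Prohibited (3.7.1) | Up to 120 mL daily | Conflict |
| Seville orange marmalade | Prohibited (3.7.1) | Up to 15 g daily | Conflict |
| Whole grapefruit | Not named (3.7.1) | Up to half a fruit daily | No direct contradiction |

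**Where the monitoring phrase fits.** The same formula heads the substrate list: "Drugs known to be substrates of CYP3A4 and/or CYP2B6, undertake appropriate monitoring if coadministration is necessary". For substrates Section 7.7 also asks only for caution, so that heading is consistent. The phrase is out of line only over the modulators. It may have been carried across from the substrate lists, but that is an inference.

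**CYP2C8 detail.** The Section 7.7 bracket reads "required washout period (5 half-lives for strong and moderate CYP3A inhibitors" and gives no length for CYP2C8. App. Table 6 names two potent inhibitors, gemfibrozil and clopidogrel, and no inducer.

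**Size for one affected patient.** Section 7.2 gives ceralasertib 160 mg once daily on Days 1-7 of each 28-day cycle: 7 × 160 mg = 1,120 mg per cycle. If a P-gp modulator is needed throughout Days 1-7, Section 7.7 withholds 7 of 7 doses, and monitoring alone withholds 0 of 7. This is the gap between the two instructions, not an estimate of harm.

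**Long-term use.** Section 3.8.1 lets one combination drug be stopped for up to 28 days and requires both to stop if one is discontinued permanently. A patient who needs a P-gp modulator indefinitely could therefore lose all study treatment under Section 7.7, yet only be monitored under the Appendix I heading.

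**The case against.** The best defence is that the two texts have different roles. Section 7.7 gives the action and cites Appendix I as a drug list, and Appendix I is titled as guidelines. Appendix I never says to continue ceralasertib, and its body text advises against co-administration. A site that follows the mandatory wording of Section 7.7 breaches nothing in the appendix, so the P-gp conflict rests on one clause in one heading. That narrows the point but does not remove it. Appendix I carries its own instructions, sites are sent there, and the heading answers the question of what to do when the drug is necessary differently from Section 7.7.

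It can also be said that Section 7.7 may not be the intended rule. The Investigator's Brochure is not among the documents, and the interactions rest on in vitro data. This stands as a reason for clinical pharmacology to confirm the rule, not for leaving two.

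Several stronger readings are tempting but not supported:

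- A reader might infer that all the grapefruit allowances contradict Section 3.7.1. That section names grapefruit juice and Seville oranges, not whole grapefruit.
- A reader might infer that the protocol nowhere says which text prevails. The end of Appendix I is not available, so this holds only for the text that is.
- A reader might rank CYP2C8 with P-gp. The compulsory trials-office contact limits how far sites can diverge.
- A reader might treat the BCRP clause as a contradiction within Section 7.7. It is unclear drafting; the action and wash-out are both stated.

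**Conclusion.** The point holds for two instructions: ceralasertib with a necessary P-gp inhibitor or inducer, and grapefruit juice and Seville orange marmalade. The CYP2C8 difference is real but minor. The BCRP wording and the missing CYP2C8 wash-out length are drafting gaps.

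The P-gp gap is at most seven doses (1,120 mg) per affected cycle, assuming the modulator is needed on every dosing day. The documents do not report how often these drugs are used, so the number of affected patients is unknown. A reader might go on to infer a biased hazard ratio or lost power; nothing in the documents supports that, and it is not claimed.

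For juice and marmalade the intended rule seems clear. The version history records the juice restriction being tightened to a prohibition at Version 3.0, and Appendix I being added later. That is background only; the conflict lies in the current text. This is a safety and consistency correction that should be made.

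**What to change.** - **P-gp:** in the Appendix I modulator heading, replace the monitoring clause with the Section 7.7 rule: interrupt ceralasertib, then wait five half-lives. Leave the substrate headings as they are.
- **BCRP:** have the sponsor's clinical pharmacology function decide whether interruption is mandatory or advisory, then use the same words in both places. A mandatory rule would reach common drugs in App. Table 8 such as omeprazole and pantoprazole.
- **CYP2C8:** replace the caution sentence in Appendix I with a cross-reference to Section 7.7, and state a wash-out length there.
- **Grapefruit:** delete the juice and Seville marmalade allowance from the App. Table 5 footnote. Either keep its limit on whole grapefruit or extend the Section 3.7.1 prohibition to the fruit. Deleting the whole footnote without that extension would remove the only limit on whole grapefruit in the available text.

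The cost is a wording amendment with no new procedure. The downside is that some patients will miss ceralasertib doses because of interactions known only from in vitro data.
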